12.0 Descriptive Factors

- 12.1 Prior treatment: 0 vs 1 vs 2 vs 3+
- 12.2 Parameters followed for hematologic response: serum monoclonal protein ≥ 0.5 g/dL and urine monoclonal protein ≥ 200 mg/24 hours vs. serum monoclonal protein ≥ 0.5 g/dL only vs. urine monoclonal protein ≥ 200 mg/24 hours only vs. serum immunoglobulin free light chain ≥ 10 mg/dL vs. bone marrow plasma cells $\geq 30\%$ vs. measurable bone or extramedullary disease on imaging. Distinguish between SPEP measurements versus quantitative IgA measurements versus quantitative IgD measurements for serum monoclonal protein.
- 12.3 mSMART FISH risk level: high risk vs low risk vs unknown.

13.0 Treatment/Follow-up Decision at Evaluation of Patient

- 13.1 Off protocol treatment

Patients who go off protocol treatment before completing 6 cycles of treatment will not continue to be followed.
- 13.2 Criteria for Treatment Discontinuation

Patients may discontinue treatment for the following reasons:

 - Progressive multiple myeloma (see Section 11.0)
 - Patient withdraws consent to continue in the trial
 - Patient develops an intercurrent illness that precludes further participation, or requires a prohibited concomitant treatment
 - The Investigator withdraws the patient in the patient's best interests
 - Patient is lost to follow-up (defined as the inability to contact the patient on 3 separate occasions)
 - Administrative reasons (e.g., the patient is transferred to hospice care)
 - An adverse event, which in the opinion of the investigator precludes further trial participation

Patients will be taken off study if they discontinue treatments for any of the reasons above.

- 13.3 Criteria for Study Discontinuation

The study may be temporarily or permanently discontinued at any site and at any time. Reasons for study discontinuation may include, but are not limited to, the following:

 - Safety concerns
 - Non-compliance with the protocol, Good Clinical Practice guidance or other regulatory requirements by the Investigator(s)
 - Request to discontinue the trial by a regulatory or health authority or an IRB

- 134 Ineligible

A patient is deemed *ineligible* if after registration, it is determined that at the time of registration, the patient did not satisfy each and every eligibility criteria for study entry.

- If the patient received treatment, the patient may continue treatment at the discretion of the physician as long as there are not safety concerns. The patient will continue in the Active Monitoring/Treatment phase of the study, as per section 4.0 of the protocol.
- If the patient never received treatment, on-study material must be submitted. No further data submission is necessary.

13.5 Major violation

A patient is deemed a *major violation*, if protocol requirements regarding treatment in cycle 1 of the initial therapy are severely violated that evaluability for primary end point is questionable. If the patient received treatment, the patient may continue treatment at the discretion of the physician as long as there are not safety concerns. The patient will continue in the Active Monitoring/Treatment phase of the study, as per section 4.0 of the protocol.

13.6 Cancel

A patient is deemed a *cancel* if he/she is removed from the study for any reason before any study treatment is given. On-study material and the End of Protocol Treatment/Intervention Form must be submitted. No further data submission is necessary.

14.0 Body Fluid Biospecimens

14.1 Summary Table of Research Blood and Body Fluid Specimens to be Collected for this Protocol

Note: Biospecimen Collection will be done under separately established IRB # 521-93 or IRB# 14-009163 or 919-04

Research	Specimen Purpose (check all that apply)	Mandatory or Optional	Blood or Body Fluid being Collected	Type of Collection Tube (color of tube top)	Volume to collect per tube (# of tubes to be collected)	Prior to D1C1	Prior to D1C2	End of treatment (optional)	Process at site? (Yes or No)	Temperatu re Conditions for Storage /Shipping
Bone marrow plasma	 Correlative  Eligibility Confirmation  Banking  Other	Mandatory	Bone marrow aspirate	EDTA (purple)	4 mL (1)	X	X	X	Yes	Cool Pack or Ice
Bone marrow cells	 Correlative  Eligibility Confirmation  Banking  Other	Mandatory	Bone marrow aspirate	ACD (yellow)	35 mL (1)	X	X	X	Yes	Cool Pack or Ice
Peripheral Blood	 Correlative  Eligibility Confirmation  Banking  Other	Mandatory	Whole Blood	ACD (yellow)	18 mL (1)	X	X	X	Yes	Cool Pack or Ice

14.2 Shipping and Handling

Kits will not be used. Each site will use their own supply of tubes

14.22 Shipping

Bone marrow and blood samples can be shipped with Cool Pak the same day they are collected (Monday-Thursday). They should be shipped priority overnight taking care to avoid Friday collection and shipping. If unavoidable, Friday shipping with Saturday delivery can be arranged contacting the laboratory in advance.

Please notify Mayo Clinic by email [contact] or [contact] to notify laboratory when specimens are being shipped.

[name]
Mayo Foundation
[name]
[name]
[name]

14.3 Metabolomics profiling

To determine if specific metabolite profiles within the bone marrow and peripheral blood plasma will be reflective of the metabolic phenotype within the clonal bone marrow plasma cells that predict for response to therapy with an IMiD.

Methodology: For this analysis, bone marrow and peripheral blood plasma will undergo large scale, untargeted metabolite profiling via liquid chromatography mass spectrometry. Differentially expressed metabolites in responder versus non-responders will be evaluated for the development of a potential biomarker predicting clinical response.

Sample type and timing: Bone marrow aspirate samples will be collected in (1) 5 ml EDTA (purple top) tube and placed on ice or a cool pack. Samples to be collected prior to cycle 1 and then prior to cycle 2.

Sample Destination:

[name]
Mayo Foundation
[name]
[name]

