14.4 Multiple myeloma cell retrieval

Samples type and timing: For studies utilizing intracellular metabolomics as well as genomics and transcriptomics of the MM cells, 35 ml of bone marrow aspirate will be obtained in (6) 6 mL ACD (yellow top) tubes in addition to the 5

ml of bone marrow aspirate from the (1) 5 mL EDTA (purple top) tube prior to cycle 1 and then prior to cycle 2.

Sample Destination:

[name]
Mayo Foundation
[name]
[name]

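### Peripheral blood plasma is to be profiled by untargeted metabolomics, but the only blood tube this protocol lists is ACD, which adds citrate and dextrose and dilutes the plasma

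*Combined protocol and SAP*

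**What the plan says.** Section 14.3 sets the assay and the two matrices: "bone marrow and peripheral blood plasma will undergo large scale, untargeted metabolite profiling via liquid chromatography mass spectrometry". It then gives the use of the data: "Differentially expressed metabolites in responder versus non-responders will be evaluated for the development of a potential biomarker predicting clinical response". The one tube it names is for marrow: "Bone marrow aspirate samples will be collected in (1) 5 ml EDTA (purple top) tube and placed on ice or a cool pack". It names no blood tube.

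Table 14.1 has three specimen rows:

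- marrow plasma: "Bone marrow aspirate EDTA (purple) 4 mL (1" mL tube entry, EDTA;
- marrow cells: ACD;
- peripheral blood: "Whole Blood ACD (yellow) 18 mL (1" tube), with no second blood row in EDTA or any other anticoagulant.

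Section 14.4 assigns the marrow ACD tubes to myeloma cell retrieval: "35 ml of bone marrow aspirate will be obtained in (6) 6 mL ACD (yellow top) tubes". For marrow, then, the protocol pairs EDTA with plasma and ACD with cells.

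Section 14.2 provides no central kit: "Each site will use their own supply of tubes". The note to table 14.1 places collection under other approvals: "Biospecimen Collection will be done under separately established IRB # 521-93 or IRB# 14-009163 or 919-04". Section 16.321 relates biomarkers to response by logistic regression and names no covariates. Nothing in Sections 14 or 16 mentions anticoagulant, dilution, fill volume or excluded features.

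**The concern.** ACD is a liquid additive whose constituents, citrate and dextrose, are themselves plasma metabolites. In an untargeted profile of ACD plasma, the citrate and glucose signals are the sum of an endogenous part and an added part, and the plan offers no way to separate them.

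Being liquid, the additive also dilutes the plasma. The red cells take up none of it, so the dilution depends on the plasma volume in the tube, and hence on hematocrit and on how far the tube was filled. Section 3.17 admits patients with hemoglobin down to 7.0 g/dL, and anemia is a listed toxicity of both IMiDs in Section 15. Hematocrit can therefore differ between patients, and within a patient between the baseline and pre-cycle 2 samples.

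What is at stake is the quality of the blood metabolite data used in the search for a response biomarker. The anticoagulant cannot be changed once the sample is drawn.

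**Working it through.** The plan states no figure on this point, so there is none to reproduce. The tube assignments come from the text; the size of the effect needs assumptions.

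**Inputs**

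- From the documents: blood in ACD, 18 mL (table 14.1); marrow plasma in EDTA (14.1, 14.3).
- Assumed, not in the documents: additive share of a full tube f = 0.10 to 0.15; hematocrit h = 0.30 to 0.45; citrate in the additive 110 mmol/L; dextrose in the additive 13 to 25 g/L, taken as anhydrous (180 g/mol), which is 72 to 139 mmol/L.

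**Step 1. Dilution of plasma at full fill**, d = f / [(1 − f)(1 − h) + f]

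| f | h | calculation | d |
|---|---|---|---|
| 0.10 | 0.30 | 0.10 / (0.630 + 0.10) | 13.7% |
| 0.10 | 0.45 | 0.10 / (0.495 + 0.10) | 16.8% |
| 0.15 | 0.30 | 0.15 / (0.595 + 0.15) | 20.1% |
| 0.15 | 0.45 | 0.15 / (0.4675 + 0.15) | 24.3% |

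**Step 2. Shift in a measured level from hematocrit alone**, 1 − (1 − d at h = 0.45) / (1 − d at h = 0.30)

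- f = 0.10: 1 − 0.832 / 0.863 = 3.6%
- f = 0.15: 1 − 0.757 / 0.799 = 5.2%

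So a patient at hematocrit 45% reads about 4-5% lower, relative, than one at 30% with the same true plasma concentration. The factor is common to all analytes that the tube does not itself add.

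**Step 3. Effect of under-filling**, with the additive volume fixed at its full-tube amount, f = 0.15 and h = 0.30: d = 0.15 / (0.15 + 0.85 × fill × 0.70)

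- full: 20.1%
- 75% fill: 0.15 / 0.596 = 25.2%
- 50% fill: 0.15 / 0.4475 = 33.5%

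The documents do not say how often tubes are under-filled, so this shows direction and scale only.

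**Step 4. Added citrate and dextrose in plasma**, additive concentration × d

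- citrate: 110 × 0.137 = 15.1 to 110 × 0.243 = 26.7 mmol/L
- dextrose: 72 × 0.137 = about 10 to 139 × 0.243 = about 34 mmol/L

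The added amount is not a constant that could be subtracted. At f = 0.15, moving hematocrit from 30% to 45% changes added citrate from 110 × 0.201 = 22.1 to 26.7 mmol/L, a spread of about 4.6 mmol/L between patients before any difference in fill.

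**Step 5. Volume needed for the fix**: 4 / 18 = 22% and 5 / 18 = 28% of the present blood draw.

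**The case against.** Five points can fairly be made in the plan's defense.

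- **The tube may be specified elsewhere.** Collection runs under three separate IRB protocols that are not among the documents. Table 14.1 is a summary and is loose about tubes: it lists marrow ACD as one 35 mL entry against six 6 mL tubes in 14.4, and marrow EDTA as 4 mL against a 5 mL tube in 14.3. This stands. A reader might infer that the wrong tube is certainly in use; the documents support only that this protocol lists no other blood tube.
- **A constant additive largely cancels.** The stated analysis compares responders with non-responders, and within blood every patient has the same listed tube type. This stands too. What does not cancel is the part of the dilution that varies between patients, and the loss of citrate and glucose.
- **Blood and marrow are not tested against each other.** A reader might infer that tube type confounds a planned marrow-versus-blood comparison. Section 14.3 asks whether profiles in these plasmas reflect the plasma-cell phenotype that predicts response, and neither 14.3 nor 16.32 plans a direct comparison. It remains true that the two sets of values would not be on the same scale.
- **A spurious predictor is not shown.** A reader might infer that dilution will appear as a predictor of response in 16.321. That would require hematocrit to be associated with response, and a 4-5% shift to matter against metabolite variability. The documents give neither. Signal normalization might remove part of a common factor, but none is specified, and it could not recover endogenous citrate or glucose.
- **Few features are lost outright.** Citrate and glucose are two features in a large panel, and no section names either as a biomarker of interest. This limits the harm but does not remove it.

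**Conclusion.** The concern holds in a limited form. Followed as written, the protocol obtains blood plasma for untargeted metabolomics from ACD tubes. There are three consequences:

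- endogenous citrate and glucose in blood cannot be interpreted;
- other blood analytes carry extra variation that may track anemia and tube fill;
- blood and marrow values are not on the same scale.

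The absence of an EDTA blood tube looks more like an omission than a choice, since the marrow rows already separate plasma from cells by anticoagulant.

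The tube assignments are certain as far as this protocol goes. The dilution of about 14-24% and the hematocrit shift of about 4-5% rest on the assumed additive share and hematocrit range. That ACD supplies citrate and dextrose follows from its name and does not depend on those assumptions.

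A reader should not extend this to the primary endpoint. Response is assessed by IMWG criteria and does not use the metabolomics result, and the marrow-plasma profiling in EDTA is untouched. The point merits correction because the remedy is cheap and only works before samples are drawn.

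**What to change.** 1. Check whether the three IRB collection protocols already provide an EDTA peripheral blood tube. If they do, correcting table 14.1 and adding a line to 14.3 is enough.
2. If they do not, amend 14.1 and 14.3 to name an EDTA peripheral blood tube for metabolomics at each time point, filled with about 4-5 mL of the existing 18 mL draw. Restrict blood metabolomics to that plasma. Reconcile the marrow tube volumes and counts between 14.1, 14.3 and 14.4 in the same amendment.
3. For plasma already collected in ACD, exclude citrate and glucose features, adjust for hematocrit from the scheduled CBC nearest the draw, and do not pool it with EDTA plasma. This is only a partial repair. The plan does not say that fill volume is recorded, and Section 4.0 allows the baseline research sample up to 28 days before registration but the screening CBC only up to 14, so the two need not coincide.

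**Cost.** One different tube at the same venipuncture, no added blood volume, and a short amendment. The ACD blood available for any other purpose falls by about 22-28%; the documents describe no peripheral-cell work that depends on it, but the laboratory should confirm. Early ACD samples would be analysed separately, which reduces the number in the main blood analysis.

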14.4 Multiple myeloma cell retrieval

Samples type and timing: For studies utilizing intracellular metabolomics as well as genomics and transcriptomics of the MM cells, 35 ml of bone marrow aspirate will be obtained in (6) 6 mL ACD (yellow top) tubes in addition to the 5

ml of bone marrow aspirate from the (1) 5 mL EDTA (purple top) tube prior to cycle 1 and then prior to cycle 2.

Sample Destination:

[name]
Mayo Foundation
[name]
[name]

15.0 Drug Information

IND exempt (159997)

15.1 Lenalidomide for Oral Administration (Revlimid®)

15.11 **Background:** Lenalidomide has antineoplastic, immunomodulatory and antiangiogenic characteristics via multiple mechanisms. Lenalidomide selectively inhibits secretion of proinflammatory cytokines (potent inhibitor of tumor necrosis factor-alpha secretion); enhances cell-mediated immunity by stimulating proliferation of anti-CD3 stimulated T cells (resulting in increased IL-2 and interferon gamma secretion); inhibits trophic signals to angiogenic factors in cells. Lenalidomide inhibits the growth of myeloma cells by inducing cell cycle arrest and cell death.

15.12 **Formulation and Dispensing:** Commercially available for oral administration as: Capsules: 5 mg, 10 mg, 15 mg and 25 mg

Lenalidomide is approved for marketing only under a FDA approved, restricted distribution program called RevAssist. Physicians, pharmacies, and patients must be registered; a maximum 28-day supply may be dispensed; a new prescription is required each time it is filled; pregnancy testing is required for females of childbearing potential.

15.13 **Preparation, storage, and stability:** Store oral capsules at controlled room temperature between 15°C and 30°C (59 °F and 86 °F). Refer to labeling on the bottle for expiration date of the commercial tablets.

15.14 **Administration:** Refer to the treatment section for specific administration instructions. Administer with water. Swallow capsule whole; do not break, open, or chew.

15.15 **Pharmacokinetic information:**
Absorption: Rapid
Metabolism: Approximately two-thirds of Lenalidomide is eliminated unchanged through urinary excretion.
Protein binding: ~30%
Time to peak, plasma: Healthy volunteers: 0.6-1.5 hours; Myeloma patients: 0.5-4 hours
Half-life elimination: ~3 hours
Excretion: Urine (~67% as unchanged drug)

15.16 **Potential Drug Interactions:**
Increased Effect/Toxicity: Abatacept and Anakinra may increase the risk of serious infection when used in combination with Lenalidomide. Lenalidomide may increase the risk of infections associated with vaccines (live organism).
Decreased Effect: Lenalidomide may decrease the effect of vaccines (dead organisms).
Herb/Nutraceutical Interactions: Avoid echinacea (has immunostimulant properties; consider therapy modifications).

15.17 **Known potential adverse events:** Consult the package insert for the most current and complete information.

Boxed Warnings:

1. Potential for human birth defects
2. Hematologic toxicity (neutropenia and thrombocytopenia)
3. Deep Venous Thrombosis and Pulmonary Embolism

Common known potential toxicities, > 10%:

Cardiovascular: Peripheral edema
Central nervous system: Fatigue, pyrexia, dizziness, headache
Dermatologic: Pruritus, rash, dry skin
Endocrine & metabolic: Hyperglycemia, hypokalemia
Gastrointestinal: Diarrhea, constipation, nausea, weight loss, dyspepsia, anorexia, taste perversion, abdominal pain
Genitourinary: Urinary tract infection
Hematologic: Thrombocytopenia, neutropenia, anemia, myelosuppression is dose-dependent and reversible with treatment interruption and/or dose reduction
Infection, especially when white blood cell count is low
Neuromuscular & skeletal: Muscle cramp, arthralgia, back pain, tremor, weakness, paresthesia, limb pain, muscle spasms
Ocular: Blurred vision
Respiratory: Nasopharyngitis, cough, dyspnea, pharyngitis, epistaxis, upper respiratory infection, pneumonia, shortness of breath

Less common known potential toxicities, 1% - 10%:

Cardiovascular: Edema, deep vein thrombosis, hypertension, chest pain, palpitation, atrial fibrillation, syncope
Central nervous system: Insomnia, hypoesthesia, pain, depression
Dermatologic: Bruising, cellulitis, erythema
Endocrine & metabolic: Hypothyroidism, hypomagnesemia, hypocalcemia
Gastrointestinal: Vomiting, xerostomia, loose stools
Genitourinary: Dysuria
Hematologic: Leukopenia, febrile neutropenia, Lymphopenia
Hepatic: ALT increased, abnormal hepatic function tests
Neuromuscular & skeletal: Myalgia, rigors, neuropathy
Respiratory: Sinusitis, rhinitis, bronchitis, pulmonary embolism
Miscellaneous: Night sweats, diaphoresis, fever

Rare known potential toxicities, <1% (Limited to important or life-threatening):

Angioedema, Stevens-Johnson Syndrome and Toxic Epidermal Necrolysis, Tumor Lysis Syndrome, Graft vs. Host Disease, rhabdomyolysis, Kidney damage which may require dialysis

15.18 **Drug procurement:** Commercial supplies. Pharmacies or clinics shall obtain supplies from normal commercial supply chain or wholesaler.

As a requirement of the REMS program, access to Lenalidomide is restricted. Lenalidomide is approved for marketing only under a FDA approved, restricted distribution program called REVCLIMID REMS (www.REVCLIMIDREMS.com) formerly known as the RevAssist program. Physicians, pharmacies, and patients must be registered; a maximum 28-day supply may be dispensed; a new prescription is required each time it is filled; pregnancy testing is required for females of childbearing potential.

15.19- Nursing Guidelines-Lenalidomide

- 15.191 Myelosuppression is dose-dependent and reversible with treatment interruption and/or dose reduction. Monitor CBC w/diff regularly. Instruct patient to report any unusual bruising or bleeding (thrombocytopenia); signs and symptoms of infection (neutropenia); and energy conserving lifestyle (anemia).
- 15.192 Lenalidomide can have thrombotic adverse events (i.e DVT and PE). Instruct patient to report any limb swelling or pain, and to seek medical attention for shortness of breath or chest pain.
- 15.193 Because of the potential for birth defects patients should be instructed in effective methods of birth control. Female patients should use 2 forms of birth control during treatment and for 4 weeks after discontinuing therapy. Males must be instructed to use a latex condom during any sexual contact with a woman of child bearing potential (even if they have had a vasectomy), because it is unknown if lenalidomide is present in semen.
- 15.194 Patients may experience pruritus, rash and dry skin. Because of the rare risk of Steven's Johnson Syndrome, patients should immediately report any rash to their provider.
- 15.195 Drug may cause hyperglycemia. Patients with diabetes or impaired fasting glucose may need to have their glucose levels monitored more closely.
- 15.196 Gastrointestinal side effects (diarrhea, constipation, nausea, dyspepsia, anorexia, etc) are commonly seen. Manage patient symptomatically and monitor for effectiveness.
- 15.197 Patients may experience myalgias, arthralgias, parasthesias and other generalized pain. Administer analgesics as ordered and monitor for their effectiveness. Rarely infective bursitis and arthritis have been reported. Instruct patients to report any joint pain or redness to study team immediately.
- 15.198 Upper respiratory symptoms (nasopharyngitis, cough, epistaxis, etc.) can be seen. Manage symptomatically and monitor for effectiveness.
- 15.199 Agent may cause fatigue, dizziness, vertigo or blurred vision. Instruct patients to use caution when driving or operating machines.
- 15.200 Monitor LFT's and report any elevations to the study team. Instruct patient to report abdominal pain and/or jaundice to the study team.
- 15.201 All prescribers and patients must be enrolled into the REVCLIMID REMS program. Only enough lenalidomide for one cycle of therapy will be supplied to the patient each cycle.

- 15.202 Rarely secondary malignancies have been seen after lenolidamide therapy, including MDS, squamous/basal cell carcinomas of the skin, T-cell type acute leukemia.
- 15.203 Monitor Renal function, renal failure has been reported.
- 15.204 Acute GVHD following Allo Transplant has been seen.
- 15.205 Rarely tumor lysis syndrome has been seen. Monitor appropriate TLS labs and report any abnormalities to the study team.

15.2 Pomalidomide (CC-4047, Pomalyst®)

15.21 **Background:** Pomalidomide (CC-4047) is a novel drug in the class of immunomodulatory agents known as IMiDs compounds. Pomalidomide binds to its molecular target cereblon (CRBN), a protein that is part of an E3 ubiquitin ligase complex, which is responsible for the polyubiquitination of substrate proteins, targeting them for subcellular redistribution and destruction by the proteasome. The pharmacologic properties of pomalidomide are of potential therapeutic benefit in the treatment of various hematologic neoplasms (such as multiple myeloma and myeloproliferative neoplasm-associated myelofibrosis), non-neoplastic hematologic disorders (such as β -thalassemia and sickle cell disease) and non-hematologic disorders such as systemic sclerosis, as well as solid tumor neoplasms.

15.22 **Formulation:** Pomalidomide capsules can be 0.5-mg gelatin capsules (size 4 reddish brown), 1-mg hard gelatin capsules (size 4 reddish brown), 2-mg (size 2 reddish-brown), 3-mg and 4-mg hard gelatin capsules (size 2 reddish-brown), and 5-mg hard gelatin capsules (size 1 reddish-brown), containing pomalidomide, mannitol, pregelatinized starch, and sodium stearyl fumarate.

Pomalidomide capsules are supplied in high density polyethylene (HDPE) containers fitted with induction seals and child-resistant plastic closures or PVC/PCTFE blister with push-through foil.

15.23 **Preparation and storage:** Store drug at controlled room temperature, between 68-77 °F (20-25°C) or as indicated on the manufacturer's label. The expiration date is indicated on the label.

Only enough study drug for one month of therapy may be dispensed.

15.24 **Administration:** Pomalidomide is administered by mouth at approximately the same time each day. Capsules should be swallowed whole, and should not be broken, chewed or opened. If a dose of pomalidomide is missed, it should be taken as soon as possible on the same day. If it is missed for the entire day, it should not be made up. Patients should be instructed never to give this medicinal product to another person and to return any unused capsules to the study doctor at the end of treatment. Patients who take more than the prescribed dose of pomalidomide should be instructed to seek emergency medical care if needed and contact study staff immediately.

15.25 **Pharmacokinetic information:**

a) Absorption – oral absorption has been moderately rapid with first dose C_{max} occurring in 1.5 to 4 hrs. More than 70% of the pomalidomide dose is absorbed

in humans. A high fat meal decreased the rate of absorption but had minimal effect on overall extent of absorption; therefore drug may be administered without regard to food intake.

b) Distribution – Apparent volume of distribution in healthy subjects ranged from 74-138 L across a dose range of 1 to 10 mg daily.

Pomalidomide protein binding in human plasma is low to moderate (15.8% for R-enantiomer, 42.2% for S-enantiomer) and the binding is concentration independent in the concentration range of 30 and 1000 ng/mL. Drug distributes into semen.

c) Metabolism – Eight metabolites were detected in plasma, each at exposures < 10% of the plasma pomalidomide. CYP-dependent metabolites accounted for approximately 43% of the excreted radioactivity, while non-CYP dependent hydrolytic metabolites accounted for 25%, and excretion of unchanged pomalidomide accounted for 10%.

d) Excretion – In healthy patients, 72.8% of the dose was recovered in urine and 15.5% was recovered in feces. Less than 3% of the dose is excreted as unchanged pomalidomide in the urine. The geometric mean terminal elimination half-life ($t_{1/2}$) of pomalidomide was approximately 7.5 hours.

In pomalidomide renal studies, no dose adjustment was required for subjects with renal impairment. On hemodialysis days, subjects were instructed to take pomalidomide following hemodialysis. No dose adjustment of pomalidomide is required for patients with hepatic impairment as defined by the Child-Pugh criteria.

15.26 Potential Drug Interactions: Pomalidomide is partially metabolized by CYP1A2 and CYP3A4/5. Pomalidomide is also a substrate for P-glycoprotein (P-gp). Coadministration of pomalidomide with the strong CYP3A4/5 and P-gp inhibitor ketoconazole, or the strong CYP3A4/5 inducer carbamazepine, had no clinically relevant effect on exposure to pomalidomide. Coadministration of the strong CYP1A2 inhibitor fluvoxamine with pomalidomide increased mean exposure to pomalidomide by 125% compared to pomalidomide alone. If strong inhibitors of CYP1A2 are coadministered with pomalidomide, the pomalidomide dose should be reduced 50%.

Smoking: Administration of pomalidomide in smokers, with smoking tobacco known to induce the CYP1A2 isoform, had no clinically relevant effect on exposure to pomalidomide relative to that exposure to pomalidomide observed in non-smokers.

Dexamethasone: Co-administration of multiple doses of 4 mg pomalidomide with 20 mg to 40 mg dexamethasone (a weak inducer of CYP3A) to patients with multiple myeloma had no effect on the pharmacokinetics of pomalidomide compared with pomalidomide administered alone.

15.27 Known potential toxicities:

Very common known potential toxicities, $\geq 10\%$:

Anemia, leukopenia, neutropenia, thrombocytopenia, constipation, diarrhea, nausea, fatigue, peripheral edema, pyrexia, bronchitis, pneumonia, upper respiratory tract infection, decreased appetite, bone pain, muscle spasm, dizziness, peripheral neuropathy, blood creatinine increased, acute renal failure,

cough, dyspnea, pruritis

Common known potential toxicities, $\geq 1\% - < 10\%$:

Febrile neutropenia, pancytopenia, vertigo, vomiting, gastrointestinal hemorrhage, hemorrhoidal hemorrhage, rectal hemorrhage, hematochezia, gingival bleeding, bronchopneumonia, herpes zoster, nasopharyngitis, neutropenic sepsis, respiratory tract infection, alanine aminotransferase increased, increased liver function test, aspartate aminotransferase increased, gamma-glutamyltransferase increased, neutrophil count decreased, platelet count decreased, white blood cell count decreased, hyperkalemia, hyponatremia, depressed level of consciousness, peripheral sensory neuropathy, paresthesia, gait disturbance, polyneuropathy, hypoesthesia, neuralgia, peripheral motor neuropathy, tremor, confusional state, renal failure, renal impairment, hypercreatininemia, urinary retention, pelvic pain, pulmonary embolism, pruritis generalized, rash, swelling face, face edema, deep vein thrombosis

Uncommon and rare known potential toxicities, $< 1\%$:

Melena, Mallory-Weiss syndrome, upper gastrointestinal hemorrhage, mucosal hemorrhage, hyperbilirubinemia, blood bilirubin increased, transaminases increased, blood alkaline phosphates increased, liver function test abnormal, basil cell carcinoma, dysesthesia, areflexia, motor dysfunction, sensory disturbance, burning sensation, muscle atrophy, blood urea increased, creatinine renal clearance decreased, oliguria, glomerular filtration rate decreased, renal tubular necrosis, acute prerenal failure, azotemia, pneumonitis, interstitial lung disease, pruritis generalized, angioedema, urticarial, eyelid edema,

Frequency not defined:

Hepatitis, hepatitis B viral reactivation, tumor lysis syndrome, squamous cell carcinoma of skin, eye swelling, periorbital edema, lip swelling, swollen tongue, mouth edema, pharyngeal edema, Stevens-Johnson syndrome, toxic epidermal necrolysis, drug reaction with eosinophilia and systemic symptoms (DRESS)

All study participants must be registered into the mandatory POMALYST REMSTM program, and be willing and able to comply with the requirements of the POMALYST REMSTM program. Females of reproductive potential must adhere to the scheduled pregnancy testing. Females of childbearing potential should not handle or administer pomalidomide unless they are wearing gloves.

15.28 **Drug procurement:** Commercial supplies. Pharmacies or clinics shall obtain supplies from normal commercial supply chain or wholesaler.

Per the standard POMALYST REMSTM program requirements, all physicians who prescribe pomalidomide for research subjects enrolled into this trial, and all research subjects enrolled into this trial, must be registered in and must comply with all requirements of the POMALYST REMSTM program.

15.29 **Nursing Guidelines**

15.259 Agent is known to be teratogenic in rabbits. Therefore all women who are pregnant or who could become pregnant, should not handle the agent

outside of the original packaging. Chemotherapy gloves should be worn if contact is necessary.

- 15.260 Because of the similarity of this agent to thalidomide certain precautions MUST be employed by all subjects on protocol and for 4 weeks after discontinuation of agent. Instruct patients the following must be adhered to: No donation of tissue/blood/semen/sperm; sexually active males/females must use protocol-specific contraception (regardless of fertility status-i.e. history of vasectomy).
- 15.261 Cytopenias are common (neutropenia most common). Monitor CBC closely and instruct patient to report any signs/symptoms of infection or unusual bruising or bleeding to the study team.
- 15.262 Thrombotic events have been reported. Anticoagulation prophylaxis may be recommended. Instruct patients to report any problems with bleeding, extremity pain or swelling, or shortness of breath to the study team immediately.
- 15.263 Patients may experience cough, URI, pneumonia, or sinusitis. Instruct patients to report respiratory symptoms to the study team.
- 15.264 Gastrointestinal side effects consisting of diarrhea, constipation, stomatitis, nausea, decreased appetite, and abdominal pain have been seen. Treat symptomatically and monitor for effectiveness.
- 15.265 Drug should be taken without food (at least 2 hours before or 2 hours after a meal). Do not open or crush capsules.
- 15.266 Patients may experience myalgias and muscle spasms. Treat symptomatically and monitor for effectiveness.
- 15.267 Fatigue is common. Instruct patient in energy conserving lifestyle.
- 5.199b Warn patients about the possibility of peripheral neuropathy, headache, confusion, and dizziness.
- 15.199c Patients may experience URI, pneumonia, dyspnea, and cough. Instruct patients to report respiratory symptoms to the study team.
- 15.199d Severe dermatologic reactions have been seen (including urticaria). Instruct patient to report and rash or skin changes to the study team.
- 15.199e All patients must be registered in the POMALYST REMS program. See protocol for more details.
- 15.99f Monitor creatinine, as patients may experience elevated creatinine levels, with rare reports of renal failure.

15.199g Rare reports of GI bleeding have been seen. Instruct patient to report any hematochezia, or melena to the study team immediately.

